## RISKS AND DISCOMFORTS

### Blood drawing/IV Placement

Phlebotomy does involve a mild stinging or painful sensation, and a very small risk for clot or infection. Standard sterile precautions will be taken to minimize this risk. On rare occasions, a hematoma or phlebitis may occur. In most circumstances, these complications resolve spontaneously or with local heat application.

Over the course of the entire 6-8 week study, we anticipate drawing approximately 450 mL of blood split over 5 study visits. By contrast, the Red Cross permits donation of 473 mL of blood (1 pint) in one session every 8 weeks.

### Eplerenone

*Common (But uncommon in healthy individuals with normal kidney function at doses used in this study):*

Hyperkalemia  
Hypotension

*Uncommon/Rare:*

Dizziness and fatigue  
Hyponatremia  
Breast pain  
Gynecomastia  
Hypercholesterolemia  
Diarrhea  
Abdominal pain  
Abnormal vaginal bleeding  
Elevated creatinine  
Albuminuria  
Cough  
Flu-like syndrome  
Angioneurotic edema  
Elevated BUN  
Elevated liver function tests  
Rash  
Elevated uric acid

## Amiloride

*Common (But uncommon in healthy individuals with normal kidney function at doses used in this study):*

- Hyperkalemia
- Hypotension

*Uncommon/Rare:*

- Gynecomastia
- Hyperchloremic metabolic acidosis
- Hyponatremia
- Abdominal pain
- Change in appetite
- Constipation
- Diarrhea
- Gas pain
- Nausea and vomiting
- Impotence
- Muscle cramps and weakness
- Cough
- Dyspnea

## Cinacalcet

*Common (But uncommon in individuals with P-HPTH at doses used in this study):*

- Hypocalcemia

*Uncommon/Rare:*

- Hypotension
- Headache
- Fatigue
- Depression
- Nausea
- Vomiting

Diarrhea  
Anorexia  
Constipation  
Abdominal pain  
Loss of appetite  
Backache  
Fracture of bone  
Spasm  
Asthenia  
Tingling sensation

Wash-out period: Subjects may experience transient elevations in their BP if they need to stop an antihypertensive per the study protocol. The principal investigator and his group have an established protocol to safely monitor BP during these times and have used this in many prior similar studies (see detailed safety protocol above). In our experience, most patients undergoing the washout protocol will remain within the target BP range; for those who required doxazosin therapy, it is anticipated that with very low doses of doxazosin the target BP will be achieved.

### Doxazosin

#### *Common*

Hypotension

#### *Uncommon*

Nasal congestion

Rash

Angioedema

Dizziness, headache, vertigo

Drowsiness

## Fatigue

Pregnancy/Fetus: Pregnant women are at risk, and therefore excluded from this study, given the use of medication intervention. Women who are breast feeding are also excluded. None of the medications used in this study are recommended for pregnancy unless specifically necessary on a case by case basis. In particular, eplerenone can be teratogenic. All women of child-bearing age, age 18- 50, will therefore be counseled on the importance of abstinence and use of barrier or hormonal contraception during the study. Further, urinary pregnancy tests will be conducted at screening and at each study visit.

Menopausal women who have not had a period for the past 12 months or more, will not need to have a pregnancy test. Also, participants who have had any well-documented method of surgical sterilization, will not need to have a pregnancy test. Methods of surgical sterilization include having had a hysterectomy, bilateral oophorectomy, a tubal ligation, or transvaginal occlusion. All other female participants must have a negative pregnancy test before starting the study drug.

Females who are sexually active and able to become pregnant, must agree to use an approved method of birth control for the entire study and for at least 1 month after their last dose of study drug. Abstinence, condoms, diaphragms, birth control pills, birth control patches and birth control injections will be considered acceptable methods. If the participant plans to use a birth control pill, patch or injection, they will be instructed to start using it at least one month before the washout period.

Privacy/Confidentiality: Subjects will be counseled regarding the importance of patient confidentiality and privacy of their health and research records. Subject information will be kept in de-identified databases and all laboratory tests will be identified through this code that will be stored on a secure Partners computer and accessible only to the PI and the main research coordinator of the study. Information regarding study outcomes can be shared with the subject's primary or specialty providers with their consent.

Tissue/DNA: For those subjects undergoing parathyroidectomy, discarded tissue will be collected, when possible, to conduct molecular and expression studies. These tissues will again be de-identified. Expression studies in the future may involve large quantities of sequencing, and in theory, there is a risk that information from studies involving genetic material may influence insurance companies and/or employers regarding patient health. To safeguard from this, no results of these molecular studies or sequencing analyses will be placed in patient charts.

### **Allergic Reactions**

As with any drug, an allergic reaction can occur. Allergic reactions can be mild or serious, and can even result in death in some cases. Common symptoms of an allergic reaction are rash, itching, skin problems, swelling of the face and throat, or trouble breathing.

### **Unknown Risks**

There may be other risks or side effects that are not known at this time.

## **BENEFITS**

There is no direct benefit from participating in this study. Subjects who participate will be clearly informed that they are not being treated for any specific medical condition, but rather are volunteering for a study that is evaluating a potential novel medical treatment for P-HPT. That being said, all participating subjects will in fact receive 2 weeks +/- 3 days of cinacalcet therapy, which is a proven and safe medical treatment to lower PTH and calcium in P-HPT. Therefore, subjects will be informed that they may receive some transient benefit in their P-HPT for 2 weeks +/- 3 days in this study, but the main objective of the study is not to be a "treatment study."

To society, if our study aims were proven correct, the results would provide a novel medical therapy for primary hyperparathyroidism with new molecular insights into disease etiology. Because P-HPT is such a common epidemiologic occurrence, evidence of a therapy to reduce PTH levels would be beneficial to society as a whole.

## **EQUITABLE SELECTION OF SUBJECTS**

This study will exclude children below the age of 18. This exclusion is primarily for safety reasons – young children should not receive eplerenone during puberty. Further, the hormonal milieu in growing pubescent children is ever-changing, and therefore, from a scientific standpoint only grown adults are included.

We will not exclude any gender or racial/ethnic demographic. However, it is well established that P-HPTH affects women far more than men, and affects white women more than other racial/ethnic demographics, and generally occurs in older age (>40 years). Therefore, it is anticipated that the majority of enrollees will be older, white, women. We anticipate that the study population will reflect the greater metropolitan Boston area that is afflicted with P-HPTH as our recruitment will focus on patients at BWH and MGH.

Elderly individuals (>80 years of age) are being excluded to reduce the incidence of other co-morbid conditions that may increase the risk of adverse events.

## **RECRUITMENT PROCEDURES**

The study will take place at BWH. Our research team has extensive experience and an established infrastructure for recruiting subjects with P-HPTH. Participants will be recruited from 4 sources:

- 1. Brigham and Women's Hospital (BWH) Endocrinology Division:* The PI has developed a system to identify and potential subjects with P-HPTH in conjunction with clinical colleagues in his division. Clinicians in the division will be made aware of the study so that they may inform their potentially eligible patients that there is a research study that may be of interest to them. Flyers and advertisements will be provided to division clinicians to give to potentially interested patients. Research coordinators for our study will be present and available to talk to any patients that have indicated to their physician that they are interested in learning more about the study. If a physician in the division discusses the study with their potentially eligible patient, and the patient expresses interest in learning more, they will be contacted by the study team via telephone. If a physician has a potentially eligible patient but has not had the opportunity to discuss the study with them in person, we will send a letter to the patient, cosigned by their

physician and the PI of this study, informing them of their potential eligibility. In the letter, participants will be given our contact information if they are interested, and will be notified that we will call them to provide information about two weeks after receipt of the letter. Patients may contact us with questions or to opt out of receiving further information about the study. [name] will inform his own patients that he is conducting a study for which they might qualify. He will offer his patients the opportunity to take home the Consent Form, and call back if they wish to participate. If the patient expresses interest, study co-investigators ([name]) will be available to discuss the study in more detail and answer any questions the patient might have. This will reduce the possibility of patients feeling obligated to participate because their own physician is asking.

2. *BWH Department of Endocrine Surgery:* The PI works closely with the endocrine surgeons at BWH where a large number of patients with P-HPT exist. Similarly to #1, parathyroid surgeons will inform their potential patients about our research study and provide them with our contact information and flyers. Our research coordinators will similarly be available to talk with potentially interested patients once they have discussed with their surgeon that they are interested in learning more. Also, with the permission of the surgeons, our study advertisement may be sent to patients in a patient-packet that is currently sent out by the Endocrine Surgery department prior to surgery consults. This advertisement will include the study coordinator's contact information and will give participants the opportunity to contact us directly to hear more about the study or to opt out.

3. *Massachusetts General Hospital (MGH) Endocrinology Division:* The PI's co-investigator, [name], is a parathyroid specialist at MGH who sees a large volume of patients with P-HPT. A similar recruiting effort to the one at the BWH Division of Endocrinology will be implemented at the MGH division of endocrinology. [name] will inform his own patients that he is conducting a study for which they might qualify. He will offer his patients the opportunity to take home the Consent Form, and call back if they wish to participate. If the patient expresses interest, study co-investigators ([name]) will be available to discuss the study in more detail and answer any questions the patient might have. This will reduce the possibility of patients feeling obligated to participate because their own physician is asking.

Similar to the strategy outlined at the BWH endocrine division, physicians may discuss the study with potentially eligible patients and those patients will be contacted with details about the study if they give permission to do so. Cosigned letters from the PI and physician may be sent to patients describing the study as outlined above.

**4. MGH Department of Surgery:** A similar recruiting effort to the one at the BWH Surgery Department will be implemented at the MGH surgery department.

Potentially eligible subjects may be pre-screened by telephone or Doximity Dialer to further determine eligibility. A member of the study staff will conduct this phone screen according to the approved telephone script and screening form.

The PI, Co-I, or research coordinator (with EPIC and HIPAA training) will also use the Research Patient Data Registry (RPDR) to identify potential research participants (between the ages of 18-80 with a diagnosis of primary hyperparathyroidism). This database would include the Brigham & Women's Hospital and Partners affiliates i.e. Faulkner Hospital, MGH, Newton Wellesley, etc. Once we have identified potentially eligible patients, we will identify whether they have indicated a "RODY YES" or a "RODY NO" response through the Research Opportunities Direct to You (RODY) program, which allows a patient to agree to be contacted directly by researchers without involving their clinician. For patients that have indicated a "RODY YES" response, we will send them a recruitment letter inviting them to participate in our study. For the "RODY NO" patients, we will identify their primary care physician, or endocrinologist, or other internist with close ties to the patient in our system, and request permission to contact their patient with our IRB approved letter (co-signed by the PI and physician) including information regarding the study. See consent procedures for other details. The letter is used to ask their permission to send their patients a co-signed letter inviting them to learn more about and potentially participate in our study. In the letter, participants will be notified that we will be calling about two weeks after receipt of the letter. For physicians that do not wish to co-sign our recruitment letter, we will give them the option to sign a separate letter notifying their patient of our study. If they agree, they will sign this letter which will be sent to their patient along with our recruitment letter as two separate letters. Our phone number will be provided so

individuals may contact us with questions or to opt out of receiving further information about the study.

We will also utilize the RSVP for Health Database.

Subjects will be offered a total of \$400.00 for participating in the study. This quantity is expected to compensate them for their time and transportation expenses. They will receive \$100 for completion of each study visit (A, B, C) and an additional \$100 for completion of the entire study. In addition, they will receive compensation for any parking expenses. We will reimburse the cost for bus, MBTA, commuter rail, or other public transportation expenses based on receipts that are provided by subjects. Subjects may receive additional compensation of \$50/visit for any additional visits that are triggered due to abnormal lab values.

## **CONSENT PROCEDURES**

As subjects are primarily recruited from the MGH and BWH Endocrinology and/or Surgery divisions, the medical records of potential subjects are readily available. The IRB Committee has waved the requirement to obtain informed consent and HIPAA Authorization for review of medical records, Research Patient Data Registry (RPDR) and other documents containing PHI for the purpose of identifying prospective subjects for recruitment. Medical records of potential participants will be reviewed by the PI/study physicians to determine eligibility (for example, review medical chart to evaluate for inclusion and exclusion criteria) and decide whether arranging a formal screening visit is indicated. This will ensure that only those subjects who are likely to meet all eligibility criteria can be approached about the study.

Potentially eligible patients will be contacted to schedule a formal in-person or remote screening visit, and will be mailed the full study consent form at least 24 hours prior to this visit. At this time, the study physician or PI will conduct screening procedures and review the entire consent form, including study procedures, risks, and benefits.

## **DATA AND SAFETY MONITORING**

The Principal Investigator will be responsible for reviewing the safety and/or efficacy data and determining whether the research should be altered or stopped.

Safety data will be reviewed on every case studied in the PI's monthly research group meeting. The PI's research group, the Cardiovascular Endocrinology Research Group (CERG), meets once a month on a Tuesday. The CERG includes more than 5 patient-oriented clinical investigators who are all endocrinologists with detailed knowledge of human subjects research and hyperparathyroidism and the medications used in this study. At each CERG meeting, each PI presents recruitment status, adverse events/safety issues, minor deviations, and other pertinent study-related issues to the group of PI's. Research coordinators also attend this meeting. Discussion of issues and a plan are formulated for each adverse event. The PI will be responsible for executing any plans agreed upon during these meetings.

In addition, the PI will meet his co-investigator [name] at MGH every 3 months to review study progress and safety.

## **MONITORING AND QUALITY ASSURANCE**

The Principal Investigator will be responsible for reviewing the safety and/or efficacy of the data and determining whether the research should be altered or stopped. The study staff will be responsible for monitoring and assuring the validity and integrity of the data and adherence to the IRB-approved protocol. Data collected by the Research Coordinators are independently evaluated by the principal and co-investigators. The original recording of an observation will be retained as the source document. The Principle Investigator will review all data collected on a subject with the study staff once a month. The Principal Investigator will review the accuracy and completeness of the study data and informed consent of each subject as well as adherence to the IRB-approved protocol.

All consent forms are signed by the participant and a study physician. The principal investigators, [name] MD, MMSc and [name], are responsible for monitoring and will meet weekly with study staff to discuss all subject recruitment, novel issues, study procedures and guidelines, adherence to IRB approved protocols, and any adverse events.

## **PRIVACY**

Data, in the form of pertinent history (prior medical illnesses/conditions), unique identifying personal information (name, address), clinical and anthropometric measures (height, weight, waist circumference, blood pressure), and blood samples will be collected during the study. All of the collected material will be used solely for research purposes. Data will be collected by trained staff and will be stored in locked cabinets and freezers or password-protected computer files to protect confidentiality. All identifying information on blood samples and saved data will be de-identified into a study code with the identifying link saved on a network drive on the Partners network accessible only to the PI and his research coordinator(s).

## Statistical Plan

**Analytic Plan, Sample Size and Power:** A sample size of 20 subjects per intervention arm (n=60 total) has been chosen using conservative calculations. The **primary outcome**,  $\Delta$ PTH in response to randomized drug therapy, will be analyzed using a 2-arm ANOVA analysis evaluating the difference between EPL and placebo. A 3-arm ANOVA including the amiloride arm will also be conducted. Sample size calculations are presented in **Figure** using preliminary data from the RAAS-PARC study where the  $\Delta$ PTH= -13 pg/mL was seen with RAAS inhibition in participants with P-HPTH, but also using a more conservative estimate (-9.0 pg/mL) that is 25% lower. It is expected that  $\Delta$ PTH with placebo will range from 0 to +4.57 pg/mL, and calculations have been made to anticipate that amiloride may serve as either a negative control (like placebo) or positive control (like EPL). With these conservative estimates, a sample size of 20 subjects/arm will be sufficient to demonstrate a  $\Delta$ PTH with a type I error of <0.05 and power=80%.

The **secondary outcomes**, change in calcium, will be analyzed in the same fashion as PTH. For calcium, sample size calculations are based on decreases in *total calcium* seen in the RAAS-PARC study ( $\Delta$ Ca= -0.32 mg/dL); treatment with EPL is expected to result in a much greater effect estimate. Thus, using *conservative* estimates of  $\Delta$ Ca= -0.20 to -0.32 mg/dL, a sample size of 20 subjects per intervention arm will be sufficient to achieve 80% power.

**Figure:** Sample size calculations based on  $\Delta$ PTH.

	$\Delta$ PTH	$\Delta$ PTH	$\Delta$ PTH	SD	Sample Size per Arm	
	Placebo	Amiloride	SPIRO		PWR=0.8	PWR=0.9
2-arms	0 pg/mL	-	-9.0 pg/mL	9.4	19	24
	0 pg/mL	-	-13.0 pg/mL	9.4	10	13
	0 pg/mL	0 pg/mL	-9.0 pg/mL	9.4	17	22
	0 pg/mL	0 pg/mL	-13.0 pg/mL	9.4	9	11
	0 pg/mL	-6.5 pg/mL	-13.0 pg/mL	9.4	12	15
	0 pg/mL	-9.0 pg/mL	-13.0 pg/mL	9.4	11	14
3-arms	0 pg/mL	-13.0 pg/mL	-13.0 pg/mL	9.4	9	11

**Figure:** Sample size calculation based on  $\Delta$ Ca.

	$\Delta$ Ca	$\Delta$ Ca	$\Delta$ Ca	SD	Sample Size per Arm	
	Placebo	Amiloride	SPIRO		PWR=0.8	PWR=0.9
	0 mg/dL	0 mg/dL	-0.20 mg/dL	0.21	17	22
	0 mg/dL	0 mg/dL	-0.32 mg/dL	0.21	8	10

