## **SAMPLE SIZE:**

A sample size of up to 60 total subjects has been chosen using very conservative calculations stemming from our preliminary data (see Detailed Protocol). Therefore, at most there will be 20 subjects per study arm; however, our sample size calculations suggest that we are likely to be adequately powered with a significantly smaller sample size as well. These sample size calculations to achieve sufficient power to observe the primary and secondary outcomes of the study:

- **Primary Outcome:** Change in PTH levels ( $\Delta$ PTH) following randomized drug intervention (**Figure; visits A=>B**).
- **Secondary Outcomes:** Change in serum iCa and markers of bone resorption following randomized drug intervention (**Figure; visits A=>B**).
- Exploratory Outcome 1:  $\Delta$ PTH in response to amiloride therapy (**Figure; visits A=>B**)
- Exploratory Outcome 2:  $\Delta$ PTH in response to combination drug therapy with EPL+ cinacalcet (**Figure; visits A=>B**).
- Exploratory Outcome 3: Correlation of eplerenone-induced  $\Delta$ PTH with MR expression from adenomatous/ hyperplastic parathyroid glands of subjects that undergo parathyroidectomy following study completion.

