**INCLUSION CRITERIA:** The target study population is healthy individuals with **a physician diagnosis of active and untreated P-HPT**. P-HPT will be classified as: Serum calcium > upper limit of reference range (ULRR) **AND** serum PTH > ULRR; or Serum Calcium > ULRR **AND** serum PTH > 30 pg/mL; or Serum Calcium within 0.2 mg/dL of the ULRR and PTH>ULRR. Subjects with multiple endocrine neoplasia or recurrent P-HPT following parathyroidectomy will be included since their response to PTH lowering therapy does not differ when compared to sporadic forms of P-HPT. Subjects with hypertension will be included if their blood pressure is <150/90 mmHg. However, since it is known that ACE inhibitors and ARB's can influence PTH and that the combination of MR antagonists and ACEi/ARB medications can increase the risk of electrolyte disturbances, subjects on an ACEi or ARB will be asked to discontinue these medications for 2 weeks prior to study initiation and during the course of the study. We expect it to be very rare that a potential participant already be prescribed an MR antagonist (such as spironolactone or eplerenone) or an ENaC inhibitor (such as amiloride or triamterene); however, in these rare instances participants may still participate after a 2 week washout of these medications. Due to the potassium sparing effects of the possible study medications eplerenone/amiloride, subjects taking potassium supplements at the time of enrollment may also be asked to stop their potassium supplement (their potassium will be measured throughout our protocol, every 1-2 weeks, as part of our elaborate safety monitoring). For subjects undergoing a washout of an anti-hypertensive medication, during this medication washout, they will be prescribed doxazosin, an alpha-antagonist that does not interact with the RAAS or PTH, **if needed**, for BP control to 105-150/50-90 mmHg, as the PI has safely performed in multiple prior

research protocols (see details below). Once the study interventions are initiated (below), doxazosin will be lowered or stopped if target BP is maintained. Women of child-bearing age (age 18-50) must have a negative pregnancy test.

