  - **Visit C:** 2 weeks +/- 3 days later to assess study outcomes following cinacalcet add-on therapy. Additional safety visits are involved (black diamonds in **Figure**).

- **Study Drug Interventions:** Enrolled subjects will undergo detailed measurements of outcome variables (see detailed outcome variables below) to establish a baseline (**Figure, visit A**). All study visits will be conducted in the morning, following at least 1 hour of monitored supine rest in the Clinical Research Center. Following study visit A, subjects will be randomized to the blinded study drug by the BWH Research Pharmacies. The initial dose of the blinded study drug will be dictated by the subject's blood pressure and the PI's clinical judgment as it relates to reasonable safety. Subjects with blood pressures near the lower range of our safety margin of 105/50 mmHg will receive the lowest dose, and subjects with higher blood pressures (or known hypertension) will receive a higher dose. The initial doses will range from: eplerenone (EPL) 12.5 mg/d to 25 mg/BID, amiloride 1.25 mg/d to 2.5 mg/BID, or placebo. The EPL arm represents the active intervention: a direct MR antagonist. The placebo arm represents a negative control. Since EPL is expected to influence more than just PTH (EPL will also decrease blood pressure and urinary excretion of potassium and calcium) when compared to placebo, the amiloride intervention represents a *second control* to provide insights into the *mechanism* by which EPL may influence PTH. Like EPL, amiloride is a potassium-sparing diuretic, with mild anti-hypertensive and hypocalciuric effects, and will therefore induce similar changes in blood pressure and urinary potassium/calcium excretion. Unlike EPL, amiloride does not directly block the MR. Rather, it blocks epithelial sodium transport channels (ENaC) in the renal distal tubule (and vascular epithelium).

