- *Outcome assessment:* The following measurements will be obtained while fasting at every study visit (**A, B, C**): serum PTH, iCa and total serum calcium, serum phosphate and fibroblast growth factor-23 (FGF-23), 25(OH)D, markers of bone resorption (serum C-telopeptide, urinary N-telopeptide, tartrate-resistant acid phosphatase 5b), markers of bone formation (osteocalcin, bone-specific alkaline phosphatase, P1NP), basic metabolic panel with creatinine, plasma renin activity, serum angiotensin II and ALDO. In addition, 24h urine collections at every study visit, as described above, will be used to measure urinary sodium, potassium, calcium, magnesium, and aldosterone.

Measures of PTH and calcium will be obtained in a standardized fashion after at least 1h of supine rest, at 1h of supine rest, 2h of supine rest, and 3h of supine rest. Subjects will have the option of receiving separate venipunctures at each hour or having an IV placed in their arm for the duration of the study visit which will be used to draw aliquots every hour. The lowest PTH value will be used in analyses.

At study visit A, peripheral blood will be collected for DNA isolation. Although no genetic studies are planned at this time, this DNA will be stored to test future research hypotheses.

Parathyroid tissue will be collected from any subjects that undergo parathyroidectomy (for clinical indications determined by their providers) in the 5 years following their study completion. It is estimated that ~50% of participating subjects may have a surgical parathyroidectomy in the 5 years following their study completion. If the surgery occurs at BWH or MGH, tissue will be collected and flash frozen in liquid nitrogen in the operating room and stored in the BWH pathology

repository, and also formalin fixed in paraffin. Samples will be analyzed for mRNA and protein expression of MR to determine whether there is a correlation of eplerenone-induced  $\Delta$ PTH with MR expression from adenomatous/ hyperplastic parathyroid glands of subjects that undergo parathyroidectomy following study completion. If the surgery occurs at a non-Partners institution, formalin fixed paraffin embedded blocks of tissue will be requested to core a sample and return the block.

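### The planned ANOVA on change in PTH is valid, but an ANCOVA with visit A PTH as covariate would protect against chance baseline imbalance at almost no cost

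*SAP*

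**What the plan says.** The SAP (Statistical Plan) states that the primary outcome "will be analyzed using a 2-arm ANOVA analysis evaluating the difference between EPL and placebo". It adds a 3-arm ANOVA including amiloride, and says that the secondary outcome, "change in calcium, will be analyzed in the same fashion as PTH". No baseline covariate is named in the supplied text.

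The sample-size table in the same section takes 0 pg/mL on placebo against -9.0 or -13.0 pg/mL on active drug, with SD 9.4. The first case needs 19 per arm for 80% power, and 20 per arm are planned.

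Four statements in the protocol matter here:
- Outcome assessment: "The following measurements will be obtained while fasting at every study visit". PTH is on that list, and "The lowest PTH value will be used in analyses".
- Study Drug Interventions: "Following study visit A, subjects will be randomized to the blinded study drug by the BWH Research Pharmacies". Visit A PTH therefore precedes randomization.
- Inclusion Criteria: patients qualify by several routes, including high calcium with "serum PTH > 30 pg/mL; or Serum Calcium within 0.2 mg/dL of the ULRR and PTH>ULRR". No upper limit on PTH is stated.
- Sample Size: "our sample size calculations suggest that we are likely to be adequately powered with a significantly smaller sample size as well".

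**The concern.** Analysing the change score is the same as adjusting for visit A PTH with a slope fixed at 1. If the slope of visit B PTH on visit A PTH is not 1, the treatment estimate still depends on any chance difference between the arms at visit A, by (1 - slope) × imbalance.

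With a slope below 1, the planned analysis understates the effect when EPL happens to start lower and overstates it when EPL starts higher. With a slope of 1 there is no shift, and above 1 the direction reverses.

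With 20 per arm such imbalances are not rare, and the randomization text supplied mentions no stratification by baseline PTH. The supplied plan has no adjusted estimate to set beside the planned one, so an adjustment made after an imbalance is seen would be post hoc.

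**Working it through.** **The plan's own figure.** Inputs from the SAP table: difference 9.0 pg/mL, SD of change 9.4, type I error 5%. Sidedness is not stated. Two-sided is assumed because it reproduces the table, whereas a one-sided test would need 15 per arm. The noncentral t calculation gives 19 per arm (80% power) and 24 (90%) for 9.0, and 10 and 13 for 13.0. All four match the SAP. At 20 per arm (38 df) power for 9.0 is **83.9%**.

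**What ANCOVA changes.** Let rho be the correlation of PTH between visits A and B. The documents do not give it, so a range is assumed, with equal variances at the two visits. Then:
- Slope of B on A = rho.
- Visit A SD = 9.4 / √(2(1 - rho)).
- ANCOVA residual SD = 9.4 × √((1 + rho)/2). At rho 0.9 this is 9.4 × √0.95 = 9.16.
- Variance of the estimated difference = residual variance × (2/n) × (1 + F/(2n - 2)), where F follows an F distribution on 1 and 2n - 2 df. Power uses 2n - 3 df and is averaged over F, so the cost of estimating the slope is included.
- Shift in the planned estimate at a 0.5 SD imbalance = (1 - rho) × 0.5 × visit A SD. At rho 0.9 this is 0.1 × 0.5 × 21.0 = 1.05 pg/mL.

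**Results at 20 per arm, difference 9.0** (planned test: 83.9% throughout):

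| rho | Visit A SD (pg/mL) | ANCOVA power | Shift at 0.5 SD imbalance (pg/mL) |
|---|---|---|---|
| 0.95 | 29.7 | 83.8% | 0.7 |
| 0.9 | 21.0 | 84.7% | 1.05 |
| 0.8 | 14.9 | 86.5% | 1.5 |
| 0.7 | 12.1 | 88.4% | 1.8 |
| 0.5 | 9.4 | 91.9% | 2.35 |

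Break-even is at rho 0.94. As rho nears 1, ANCOVA power falls to 82.9%, a loss of about 1 point. A separate simulation of 20,000 trials per setting agreed (84.6% at rho 0.9, 91.7% at 0.5). It also found both analyses unbiased, with type I error of 4.7% to 5.0%.

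**How likely an imbalance is.** The standard error of the visit A difference, in SD units, is √(2/20) = 0.316. The chance of 0.5 SD or more in one direction is 1 - Φ(0.5/0.316) = 5.7%, and in either direction 11.4%.

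**Power given an imbalance of exactly 0.5 SD** (60,000 simulated trials per case):

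| rho | Planned ANOVA, EPL lower | ANCOVA, EPL lower | Planned ANOVA, EPL higher |
|---|---|---|---|
| 0.95 | 77% | 82% | 90% |
| 0.9 | 74% | 83% | 91% |
| 0.7 | 66% | 87% | 96% |
| 0.5 | 60% | 91% | 98% |

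The high figures in the last column come from an overstated effect.

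**Unequal variances** (illustrative SDs; slope = rho × SD at B / SD at A). SD 20 at A and 18 at B with rho 0.9 gives slope 0.9 × 18/20 = 0.81 and shift 0.19 × 0.5 × 20 = 1.9 pg/mL. SD 20 and 22 with rho 0.92 gives slope 1.01 and a shift of about 0.1 with the sign reversed.

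**A smaller trial.** At 10 per arm and a difference of 13.0, the planned test has 83.2% power. ANCOVA gives 81.7% at rho 0.95, 82.7% at 0.9, 84.6% at 0.8 and 90.3% at 0.5. Break-even is rho 0.87 and the floor is 80.8%, a loss of about 2.5 points.

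**Calcium** (-0.20 mg/dL, SD 0.21, EPL against placebo, 20 per arm). The unadjusted test has 83.5% power. ANCOVA gives 83.4%, 84.3%, 86.2% and 91.6% at rho 0.95, 0.9, 0.8 and 0.5.

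**The case against.** The planned analysis matches its own sample-size calculation, holds its error rate and exceeds its power target, so this is a choice between two valid methods. The larger gains come from the less plausible rows: rho 0.5 or 0.7 implies a visit A SD of only 9.4 or 12.1 pg/mL, while the inclusion criteria suggest a wide spread. At rho 0.9 to 0.95 the average gain is +0.8 to -0.1 points. At 20 per arm and a difference of 13.0, the planned test already has 98.9% power and ANCOVA adds almost nothing. The conditional figures describe an unlucky draw whose mirror image raises power. Finally, part of the SAP and the Detailed Protocol cited in the protocol were not available, so an adjusted analysis might be described there.

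Most of this stands. The average power gain may well be small, and in a much smaller trial with high rho it may be a loss. What remains is the estimate itself: unless the slope is 1, it moves with baseline imbalance whatever the power, and averaging over randomizations does not help the one trial that is run. At rho 0.9, where the average gain is under 1 point, ANCOVA still recovers about 9 points when EPL starts 0.5 SD lower (83% against 74%).

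**Conclusion.** The point holds as a low-cost improvement, not as an error; the planned sample size needs no correction on this account. At 20 per arm and a 9.0 pg/mL difference, the average effect of ANCOVA on power runs from a loss of about 1 point to a gain of 8 points (91.9% against 83.9% at rho 0.5). At the high correlations that seem plausible here it is close to nil. The firmer benefit is an estimate that does not move by roughly 0.7 to 2.4 pg/mL when the arms differ by 0.5 SD at visit A.

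These figures assume a range for rho, equal variances (except where shown), a linear relation and a two-sided 5% test. With a true slope near 1 the benefit disappears. The statement that no adjustment is planned applies only to the text supplied.

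**What to change.** Add one sentence to the SAP: the primary EPL against placebo comparison is an ANCOVA of visit B PTH (or, equivalently for the treatment effect, change in PTH) on arm, with visit A PTH as covariate, using the lowest value at each visit as the protocol defines it. Use the same model for calcium, with its own visit A value. Keep the unadjusted ANOVA as a sensitivity analysis, and plot visit B against visit A PTH to check that the relation is roughly linear.

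The cost is one degree of freedom and one estimated slope, with no new data and no change in sample size. The power at risk is about 1 point at 20 per arm, and up to about 2.5 points at 10 per arm for a 13.0 pg/mL difference. If the trial may stop well below 20 per arm, the sponsor should weigh that larger loss before fixing the primary model.
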